#### **3.1 Study Design**

This is a prospective study designed to validate the PHP by comparing its BP measurements with those from an FDA-cleared ambulatory BP cuff (Norav NBP One). The study will include 85 participants who will undergo a series of BP measurements over a 20-minute period while simultaneously wearing the PHP and ambulatory BP (ABP) cuff. This study will be conducted in home and office environments, including patients' homes and the offices of Perin Health Devices ([name]). An initial BP measurement will be taken, followed by four reference BP measurements and three paired test device measurements.

The study will also include an optional cold pressor test to further evaluate the device's performance on intra-patient variability. The cold stimulus activates afferent sensory pathways that, in turn, trigger a sympathetic response resulting in an increase in BP. If a subject elects to participate in the cold pressor test, the validation measurements will be repeated after placing their hand in ice water for one minute.

According to AAMI standards, this study design will ensure the mean absolute error (MAE) between the PHP and the reference device does not exceed 5 mmHg with a standard deviation (SD) of  $\leq 8$  mmHg for both SBP and DBP.

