5. The application site will be cleaned using an alcohol wipe and the PHP will be adhered to the participant's chest. The ABP cuff will be placed on the left arm, following the procedure outlined in their instructions for use (IFU).

---

6. The validation procedure starts with the subject seated comfortably and relaxed for at least 5 minutes, her/his back and arm supported with the middle of the upper arm at heart level, legs uncrossed, and feet flat on the floor. Talking and any other interference will be avoided throughout the entire validation procedure.
7. A timer is started and an initial measurement is taken: a reference BP measurement ( $R_0$ ) followed by a test device measurement ( $T_0$ ) to confirm the PHP function. A calibration measurement using a third BP device will be taken when  $T_0$  is taken to calibrate the PHP.
8. Four reference BP measurements follow, alternated by three test device measurements ( $R_1-T_1-R_2-T_2-R_3-T_3-R_4$ ) (See Table 1).  $R_x$  measurements will be performed with 2-minute intervals, with  $T_x$  measurements occurring 15 seconds after an  $R_x$  measurement. The recordings will be synchronized using absolute time measurements as well as a timer that is started.
9. The participant will optionally undergo the cold pressor test if they indicated on the intake form that they are willing and able to participate. If they opt not to undergo the cold pressor test, skip to Step 10. If they do opt to undergo the cold pressor test, the hand contralateral to the arm with the ambulatory blood pressure cuff will be submerged in ice water ( $\leq 5^{\circ}\text{C}$ ) for at least 1 minute. The study team member will record the temperature of the ice water at the start of the cold pressor test. The participant may opt to remove their hand at any time if they are experiencing high levels of discomfort. After 1 minute the participant will be instructed to remove their hand.
10. Validation measurements from Table 1 will be repeated as soon as the subject removes their hand. Four reference BP measurements follow, alternated by three test device measurements ( $R_1-T_1-R_2-T_2-R_3-T_3-R_4$ ) (See Table 1).  $R_x$  measurements will be performed with 2-minute intervals, with  $T_x$  measurements occurring 15 seconds after an  $R_x$  measurement.

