### 3.5 Process for Data/Specimen Procurement

- Pre-enrollment contact information and screening will be conducted over Google Forms. The information will be collected on a digital spreadsheet. The Google form is shown in Appendix E.
- Data from the ABP cuff will be collected using a PC computer program. The program will output SBP, DBP, and precise measurement time.
- Data from the PHP will be collected using a Bluetooth-enabled tablet. The tablet will provide synchronized 30-second measurements of each measurement modality (PPG, ECG, BioZ, auscultation, motion, skin temperature) sampled at their respective pre-established sampling rates and the precise measurement time.
- The intake form will be provided physically to the participants. Following the data collection, the values from the intake form will be captured in an electronic spreadsheet.
- The consent forms will be scanned and saved in a secure, encrypted folder. The physical copies of the consent forms will be returned to the participant.

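### The cold pressor block takes no reading during the stimulus and requires no BP rise to be shown, so it cannot guarantee a test of within-person tracking

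*Combined protocol and SAP*

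**What the plan says.** All references are to the combined protocol and SAP.

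- **Purpose (3.1).** "The study will also include an optional cold pressor test to further evaluate the device's performance on intra-patient variability". The mechanism given is that cold will "trigger a sympathetic response resulting in an increase in BP". No size or duration of the rise is stated.
- **Order (3.1 and 3.4).** Section 3.1 says "the validation measurements will be repeated after placing their hand in ice water for one minute". Step 9 of 3.4 ends the immersion: "After 1 minute the participant will be instructed to remove their hand". Step 10 continues: "Validation measurements from Table 1 will be repeated as soon as the subject removes their hand".
- **Schedule (3.4, step 10).** "Four reference BP measurements follow, alternated by three test device measurements", with references every 2 minutes and each patch (PHP) reading 15 s after a reference.
- **Recording length (3.5).** "The tablet will provide synchronized 30-second measurements of each measurement modality".
- **Analysis (4.1).** Mean error and SD, paired t-tests and Bland-Altman plots, judged against 5 mmHg and 8 mmHg. There is no separate analysis, pairing rule or minimum BP change for the cold pressor data.

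**The concern.** The cold pressor is the only planned BP perturbation in the study. The algorithm estimates BP from a calibration value and sensor features (4.1), and calibration is done at rest a few minutes earlier (3.4, step 7). Readings near resting BP therefore cannot separate a patch that follows BP from one that hands back its calibration value. Section 2.0 justifies the technology partly by the failure of cuffs to capture variability and rapid change, so this distinction matters.

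As scheduled, every reading comes after the stimulus has ended, and nothing in the plan checks that BP was still raised when it was measured. If the cold pressor pairs are also pooled with the resting pairs, which 4.1 does not rule out, a non-tracking device could pass and the block would appear to support tracking.

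**Working it through.** **1. The plan's own figure.** The only stated figure that bears on timing is the 20-minute monitoring period (3.1). Rest 5 + first reference to R1 2 (assumed to be the same 2-minute interval) + first block 6 + immersion 1 + second block 6 = 20 min, plus the last cuff reading. The schedule is consistent with that figure.

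**2. Where the readings fall.** Time zero is hand removal. R1 to R4 start at 0:00, 2:00, 4:00 and 6:00. Each T comes at the start of its R + cuff time + 15 s. Cuff time is not given, so 0 s and 45 s are assumed.

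| Cuff time | T1 | T2 | T3 |
|---|---|---|---|
| 0 s | 0:15 | 2:15 | 4:15 |
| 45 s | 1:00 | 3:00 | 5:00 |

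So 0 of 4 reference and 0 of 3 patch readings fall during the stimulus, and 2 of 3 patch readings start more than 2 minutes after it ends.

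**3. How much rise could remain.** Assumptions not in the documents: a 20 mmHg rise at hand removal, exponential fall, references read at 30, 150, 270 and 390 s, and patch windows centred at 75, 195 and 315 s (45 s cuff + 15 s lag + half of 30 s for the first). Rise remaining = 20 × 2^(−t/half-life), in mmHg:

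| Half-life | R1 / R2 / R3 / R4 | T1 / T2 / T3 |
|---|---|---|
| 45 s | 12.6 / 2.0 / 0.3 / 0.0 | 6.3 / 1.0 / 0.2 |
| 90 s | 15.9 / 6.3 / 2.5 / 1.0 | 11.2 / 4.5 / 1.8 |
| 180 s | 17.8 / 11.2 / 7.1 / 4.5 | 15.0 / 9.4 / 5.9 |

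For T2 to be below a quarter of the rise, the half-life must be under 2.25/2 = 1.1 min (cuff time 0 s) or 3/2 = 1.5 min (45 s). For T2 to be below half, it must be under 2.25 or 3.0 min.

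**4. Would a non-tracking device be caught?** Take a device that always returns resting BP, with no other noise. Its error in the three resting pairs is 0. Its error in each post-cold pair is minus the mean of the two adjacent references. At 90 s, for example, these are −(15.9+6.3)/2 = −11.1, −(6.3+2.5)/2 = −4.4 and −(2.5+1.0)/2 = −1.7. The mean of (0, 0, 0, −11.1, −4.4, −1.7) is −17.2/6 = −2.9, and the SD of the six values is 4.4. The pooling is an assumption.

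| Half-life | Pooled mean / SD | Post-cold pairs alone, mean |
|---|---|---|
| 45 s | −1.4 / 2.9 | −2.9 |
| 90 s | −2.9 / 4.4 | −5.7 |
| 180 s | −4.9 / 6.1 | −9.8 |

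All pooled results meet 5/8, with 180 s borderline. All errors are zero or negative, so the mean absolute error named in 1.0 has the same size as the mean error. Independent noise would add to the SD, and the room left is √(64 − SD²): 7.5, 6.7 and 5.2 mmHg.

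**5. Sensitivity.** Comparing each T with the preceding R only gives pooled means of −2.5, −4.1 and −6.0 (SD 5.0, 6.3 and 7.4), so the 180 s case fails on the mean and the other two pass. Post-cold pairs alone stay within 5 mmHg on the mean only up to a half-life of about 75 s (−4.8). The test is optional. If only half of participants took it (assumed) and the rest gave resting pairs alone, the pooled mean would be the post-cold mean × 0.5/1.5, or −1.0, −1.9 and −3.3.

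**The case against.** The strongest reply is that the documents give no decay time, and that the stated purpose is within-person variability rather than peak response. A falling series after the stimulus is within-person change. At a 90 s half-life the references run from 15.9 down to 1.0 mmHg above rest, and at 180 s all three patch readings carry more than 5 mmHg. This stands. It rules out three inferences that a reader might draw: that the rise has faded by T2 and T3, that only one pair in three carries useful change, and that the block can neither show nor refute tracking. Each needs a short half-life that the documents do not supply.

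A reader might also infer a timing bias, because T1 is taken later than R1 on a falling curve. Under the assumptions above, T1 minus R1 for a perfect device is −6.3 to −2.8 mmHg. But no passage pairs T1 with R1 alone, and Table 1 brackets every T with two references. Against their mean the error is −1.0 to +0.5 mmHg. What remains is that the pairing rule is unstated.

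The block is also optional and appears in neither the objectives (1.0) nor the acceptance criteria (4.1). That limits the weight of the point but does not remove it, because no other part of the study perturbs BP on purpose.

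**Conclusion.** The point holds in a limited form. From the text alone: no reading is taken during the stimulus, two of three patch readings start more than 2 minutes after it ends, no BP rise has to be shown, and no analysis is defined for these data. The block therefore cannot guarantee the test that 3.1 says it is for.

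The size is conditional on the 20 mmHg rise, exponential decay, absence of noise and pooling set out above. Across half-lives of 45 to 180 s, a device with no tracking ability would score −1.4/2.9 to −4.9/6.1 mmHg and meet 5/8. The longest half-life is borderline, and fails on the mean under preceding-reference pairing. This does not show that the rise is gone when measured; it shows that the plan neither ensures nor checks that it is present. The change is worth making, but the point does not undermine the main resting comparison.

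**What to change.** 1. **Section 4.1, no new data.** Analyse the cold pressor data separately, as change from each participant's resting mean, with patch change set against reference change. Compare each T with the mean of its two adjacent R readings. Report the reference BP rise actually achieved, so that a reader can see how much of a test took place. The cost is one paragraph of analysis plan.
2. **Steps 9-10 and Table 1.** Start the first cold pressor reference early enough that it and an overlapping 30 s patch recording fall as far as possible within the immersion already planned. Time the remaining readings from it at the existing 2-minute interval, so that it does not collide with an R1 at hand removal. With an assumed 45 s cuff reading and a 60 s immersion, it would have to start within 60 − 45 = 15 s. The existing 15 s lag would not fit (45 + 15 + 30 = 90 s), which is why the recordings must overlap. State in advance how this pair is compared; the natural partner is the reference that it overlaps. Keep the later readings as recovery readings that still count as within-person change.

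The first reading is moved, not added, so there is no extra cuff inflation. The downsides are that some in-immersion readings will be lost to movement or early hand removal, and that an early reading may precede the full rise, whose onset the documents do not give. Keep affected participants through their post-removal readings rather than excluding them.

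The immersion itself is not changed by this proposal. Two passages in step 9 must be reconciled by the sponsor. One sets a minimum immersion of a minute, while another has the participant told to withdraw at one minute. And those who decline are sent to step 10, which is itself the post-immersion repeat block.

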### 3.5 Process for Data/Specimen Procurement

- Pre-enrollment contact information and screening will be conducted over Google Forms. The information will be collected on a digital spreadsheet. The Google form is shown in Appendix E.
- Data from the ABP cuff will be collected using a PC computer program. The program will output SBP, DBP, and precise measurement time.
- Data from the PHP will be collected using a Bluetooth-enabled tablet. The tablet will provide synchronized 30-second measurements of each measurement modality (PPG, ECG, BioZ, auscultation, motion, skin temperature) sampled at their respective pre-established sampling rates and the precise measurement time.
- The intake form will be provided physically to the participants. Following the data collection, the values from the intake form will be captured in an electronic spreadsheet.
- The consent forms will be scanned and saved in a secure, encrypted folder. The physical copies of the consent forms will be returned to the participant.

### 3.6 Record Review

N.A., no record review will be conducted as part of this study.

### 3.7 Database Access

N.A., no access to a pre-existing database will be conducted as part of this study.

### 3.8 Data/Specimen Storage

Pre-enrollment contact information and screening questions will not be retained/stored after the conclusion of the study.

The patient will be assigned a random ID at enrollment and this random ID will be used to link the intake form, the ABP measurements, and the PHP measurements. No other identifier will be used other than the random ID. The random ID will not be included in the consent form.

Raw data will be securely retained electronically for future secondary analysis. Due to the nature of this data and the use of this data in a regulatory approval, the electronic data

---

files will be maintained. The data will be stored in a local, encrypted database located at the offices of Perin Health Devices ([name]). Physical artifacts (completed intake forms) will be stored securely in a locked filing cabinet in a private office at the offices of Perin Health Devices for three years and then destroyed.

Access to the data will be restricted to the study team. If any future or secondary analysis is conducted by other investigators, a formal approval process will be undertaken, including the validation of proper training certificates and data use plans. Training, requests, and approvals will be maintained in Perin Health Devices' electronic quality management system (eQMS). PI [name] will be responsible for the oversight of the electronic and physical data.

## 4.0 Data/Specimen Analysis

### 4.1 Data Analysis Plan

Blood pressure from the PHP will be calculated using a proprietary algorithmic approach. The steps include:

1. Preprocessing: Areas of high motion, as determined by the accelerometer measurement are excluded from the analysis. For ECG and PPG signals, artifacts such as baseline wandering and respiratory components at lower frequencies, as well as power line harmonics and electromyogram artifacts at higher frequencies are removed. Auscultation signals are filtered to remove lung sound components and concentrate on heart sound components.
2. Segmentation: Fiducials for the ECG, PPG, and auscultation signals are extracted using respective techniques.
3. Depth-Resolved PPG: The time difference between the capillary component (blue LED) and the arteriolar component (red/IR LED) is used to calculate arteriolar PTT and SVR.
4. Feature Extraction: A combination of hand-crafted features and learned feature embeddings are extracted and concatenated into a single feature vector.
5. Deep Learning Estimation: An LSTM-based model is used to estimate SBP and DBP from the calibration value and the input feature vector.

The mean error and standard deviation of the SBP and DBP measurements from the PHP relative to the ambulatory blood pressure cuff will be calculated. Statistical analysis will include paired t-tests and Bland-Altman plots to assess the agreement between the two devices.

The feature extraction and estimation analysis will be conducted by PI [name], blinded to reference values to maintain data analysis integrity, pursuant of the company's conflict of interest policies. The evaluation and statistical comparisons against the ABP cuff will be conducted by Co-I [name] with independent validation by [name], an independent reviewer. The criteria for validation will follow AAMI standards, where the mean difference must be  $\leq 5$  mmHg and the standard deviation  $\leq 8$  mmHg.

---

#### 4.2 Power Calculation

Based on the AAMI/ESH/ISO consensus standard, a sample size of 85 participants is sufficient to achieve a power of 80% with an alpha level of 0.05 to detect a mean difference in blood pressure measurements between the two devices.

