## 1.0 Objectives

The primary aim of the study is to validate a proprietary cuffless blood pressure algorithm using measurements from a chest-worn medical device, the Perin Health Patch (PHP). The study will compare the performance of the PHP to an ambulatory blood pressure cuff across 85 subjects for a 20-minute monitoring period and confirm that the wearable device performance meets AAMI standards. The specific objectives are:

- To calculate the mean error and standard deviation of blood pressure (BP) measurements from the PHP relative to the ambulatory blood pressure cuff.
- To determine the compliance of the PHP's mean absolute error (MAE) and standard deviation (SD) with AAMI standards:  $\leq 5$  mmHg MAE with  $\leq 8$  mmHg SD for systolic and diastolic BP.

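### The 80% power in 4.2 is for detecting a difference between devices, not for meeting the 5/8 mmHg rule on SBP and DBP, and 4.1 lists a paired t-test as a measure of agreement

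*Combined protocol and SAP*

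**What the plan says.** Section 4.2, citing the AAMI/ESH/ISO standard, states that 85 participants are "sufficient to achieve a power of 80% with an alpha level of 0.05 to detect a mean difference" between the two devices. It gives no size of difference, no SD of the differences, no sidedness and no unit of analysis.

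Section 4.1 plans the "mean error and standard deviation of the SBP and DBP measurements from the PHP relative to the ambulatory blood pressure cuff". It then states: "The criteria for validation will follow AAMI standards, where the mean difference must be" at most 5 mmHg, with an SD of at most 8 mmHg. Section 1.0 applies the limits to both pressures ("mmHg SD for systolic and diastolic BP").

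On analysis, 4.1 says: "Statistical analysis will include paired t-tests and Bland-Altman plots to assess the agreement between the two devices".

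On data, 3.1 says: "An initial BP measurement will be taken, followed by four reference BP measurements and three paired test device measurements". For those who take the optional cold pressor test, "the validation measurements will be repeated after placing their hand in ice water for one minute". Section 4.1 does not say whether its mean and SD are per reading or per participant.

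**The concern.** A sample-size statement should tell the reader how likely the study is to meet its own success rule if the device performs as hoped. Here the rule is to stay within two limits on two endpoints. Power to detect a difference answers another question: a device can have a readily detectable bias and still pass, or no detectable bias and fail on spread. The stated 80% therefore does not describe the chance of a pass.

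The t-test in 4.1 raises the same issue. A paired t-test asks whether the mean error is zero and does not assess the spread of individual errors, so a non-significant result is not evidence of agreement. Section 3.8 says the data will be used for regulatory approval. A power figure for the wrong hypothesis and a mislabelled p-value would both weaken that evidence.

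**Working it through.** **Inputs from the documents:** n = 85, power 80%, alpha 0.05 (4.2); limits 5 and 8 mmHg (4.1); SBP and DBP (1.0); three pairs per participant, repeated after the optional cold pressor test (3.1).

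**Assumptions, because the documents give no planning values:** normal errors, two-sided alpha, all 85 participants complete, one value per participant unless stated, and the true bias, SD and correlations shown.

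**1. The plan's own figure.** It cannot be reproduced, because no difference or SD is given. If 5 and 8 mmHg are taken as difference and SD, a two-sided paired t-test needs n = 23 for 80% power, and its power at n = 85 is above 99.9%. A two-sample t-test with the same values needs 42 per group (84 in total), but that treats the devices as independent groups, which is not this design.

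**2. What 80% power at n = 85 does fix.** Solving the noncentral t distribution (84 df, noncentrality d × √85) for 80% gives d = 0.307.
- SD 6: 0.3074 × 6 = 1.84 mmHg
- SD 8: 0.3074 × 8 = 2.46 mmHg

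Both are inside the 5 mmHg limit.

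**3. Chance of meeting the rule, one endpoint.** With bias b, true SD σ and sample SD S:

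P(pass) = P(|mean| ≤ 5) × P(S ≤ 8), where mean ~ N(b, σ²/85) and P(S ≤ 8) = P(χ²₈₄ ≤ 84 × 64/σ²).

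Example at σ = 7.5 and b = 0: 84 × 64/56.25 = 95.57, so P(S ≤ 8) = 0.818. The mean limit is met with probability close to 1, so P(pass) = 82%.

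| True SD | Bias 0 | Bias 4 |
|---|---|---|
| 6 | >99.9% | 94% |
| 7 | 97% | 88% |
| 7.5 | 82% | 73% |
| 8 | 52% | 46% |

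When bias is well inside 5 mmHg, the SD dominates. Near 5 mmHg, bias matters as much: at SD 6 the standard error is 6/√85 = 0.65, and the chance falls from 94% at bias 4 to 78% at 4.5 and 50% at 5.

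**4. Both endpoints, bias 0** (simulated, SBP-DBP error correlation 0 to 0.9): 94-95% at SD 7, 67-75% at 7.5, 27-42% at 8. With independent errors this is the square of the one-endpoint value, for example 0.818² = 0.67.

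**5. Unit of analysis.** Per reading (85 × 3 = 255 pairs, intraclass correlation (ICC) 0.3 to 0.8, one endpoint, bias 0), the chance at SD 7.5 is 92% to 86%, against 82% for one value per participant with that same SD. The unit must be known before any figure can be quoted.

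**6. t-test against the rule, one value per participant.**
- Bias 2.5, SD 7: t-test significant 90%, rule met 97%, both 88%.
- Bias 0, SD 9: t-test non-significant 95%, rule met 8%.

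The two can disagree in either direction.

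**The case against.** The strongest reply is that little turns on this. Section 4.2 attributes 85 to the cited standard, and the verdict rests on the 5/8 rule, so correcting the text changes neither the sample size nor the data nor the pass/fail decision. Section 4.1 already plans mean error, SD and Bland-Altman plots, and testing for bias beside a Bland-Altman plot is a legitimate secondary use. The standard may define the analysis unit and justify 85. The SDs above are assumed, and an accurate device passes easily: at SD 6 and zero bias the chance exceeds 99.9% even for both endpoints.

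Most of this stands, and it limits the point. The fair statement on inputs is that the protocol does not restate them; alone, that is missing detail. The t-test need not be removed if it is labelled correctly. What remains is that 4.2 goes beyond citing the standard and attaches a power figure to a hypothesis that is not the success rule.

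A reader might infer more: that 85 is too few, that the 80% is wrong, or that it came from an unpaired formula. The documents support none of these. The figure can be neither confirmed nor refuted, and they do not say how it was obtained. Nor is it right to infer that the plan lacks an agreement analysis or that the t-test decides the outcome.

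**Conclusion.** The point holds and should be fixed, as a correction to what 4.2 and 4.1 claim rather than to the size of the study. The 80% is not the chance of success. For one endpoint at zero bias that chance runs from 97% to 52% as the true SD goes from 7 to 8, and it is lower when both endpoints must pass. It depends mainly on the SD while bias is well inside 5 mmHg, and on bias as much as SD near that limit.

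These probabilities rest on the assumptions listed with the calculations. They make no allowance for readings removed for motion or signal quality under 4.1 and 4.3. They use the mean-difference form of the rule in 4.1; the mean-absolute-error wording in 1.0 and 3.1 is a separate conflict.

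**What to change.** First reconcile the mean-absolute-error wording (1.0, 3.1) with the mean-difference wording (4.1), so that there is one rule to calculate for. Then:

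1. **Section 4.2.** Remove the statement of 80% power to detect a difference. Say that 85 is taken from the cited standard. State the analysis unit. Give the probability of meeting the rule for both SBP and DBP over a stated range of true SD and bias, for example SD 6 to 8 and bias 0 to 4, with the assumed correlations.
2. **Section 4.1.** Do not use the paired t-test as evidence of agreement: drop it, or label it a test of mean bias only. Report mean error with a 95% CI clustered by participant and with repeated-measures Bland-Altman limits, as descriptive support for the existing 5/8 rule.

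**Cost.** This needs new wording, a short table and slightly more analysis, with no added participants and no new pass/fail test. The clustered CI is wider than one treating readings as independent, by about √(1 + (k − 1) × ICC) for k equally correlated readings. At an assumed ICC of 0.3 to 0.8 that is √1.6 to √2.6 = 1.26 to 1.61 with three readings, and √2.5 to √5 = 1.58 to 2.24 with six. The stated chance of passing may look less favourable if the device is near a limit.
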